## 7.1. Baseline Assessments

## 7.1.1. Baseline Data

Baseline data collection will include:

- Demographics (date of birth, sex, race/ethnicity)
- Weight, Height (calculated BMI)
- Medical history (including cardiovascular, hepatic, endocrine, secondary malignancies, renal including presence of hereditary RCC syndromes)
- RCC history, including:
  - Date of initial RCC diagnosis

b. Applicable only to sites where HRQoL questionnaires may be administered

c. Refer to Section 7.4 regarding details of the timing and nature of events to be reported.

- Date of diagnosis with advanced/metastatic RCC
- Site of metastases (lung, bone, liver, adrenal glands, CNS, lymph nodes, other)
  - Number of metastatic sites
  - Existence of measurable lesions (yes/no)
  - Whether disease status evaluation conducted as part of routine care was consistent with RECIST methods (yes/no)
- Metastasis confirmed by imaging (type, date) and by biopsy (yes/no, date)
- Other histopathology: sarcomatoid features, microvascular invasion, tumour necrosis, and invasion of the collecting system
- RCC treatment history
  - Surgical history (simple, radical or partial nephrectomy; arterial embolization; metastatic lesion resection), dates, status post-surgery
  - Radiation therapy, stereotactic radiotherapy
  - Radiofrequency or cryo-ablation
  - Previous lines of systemic therapy, including immunotherapy (e.g., interferon  $\alpha$ , IL-2)
- Performance status (ECOG and Karnofsky scales, included in Appendix 3) at enrollment, if recorded
- MSKCC and/or modified Heng risk category at enrollment (favourable/good, intermediate or poor), if recorded (for description, refer to Appendix 3)
- Initial pazopanib prescription
- Pazopanib start date
- Any changes to pazopanib dose or regimen since starting, with dates and dose changes, duration of interruption (if applicable)
- Selected concomitant medications (CYP3A4 inhibitors and inducers)
- Relevant laboratory testing (e.g., haemoglobin, platelet count, LDH, AST, ALT)
- HRQoL [EQ-5D, FKSI-19 and FACIT Fatigue scale, refer to Section 7.5], where applicable
- Occurrence of any SAEs/AESIs since starting pazopanib

# 7.2. Follow-up Assessments

Follow-up data collection will include:

- Visit date
- Current weight (kg)

- ECOG and Karnofsky scales (if recorded)/Survival status
- Date and cause of death, if applicable
- New onset co-morbidities and updated medical history
- Tumor response status
- Evidence of radiographic and or clinical progression in the opinion of the physician
  - Date of physician-identified disease progression
  - Documented signs of clinical or radiographic progression
    - Tumour response based on imaging results performed as part of standard of care
    - Clinical deterioration [symptomatic deterioration, need for palliative therapies, need for medical intervention (e.g., ER, hospitalization, surgery]
- Whether disease status evaluation as part of routine care was consistent with RECIST methods (yes/no)
- Updated pazopanib exposure
- If dose changes/discontinuations, change type, date (or duration) of change and reason for change
- Additional treatment strategies for RCC
- HRQoL [EQ-5D, FKSI-19 and FACIT Fatigue scale, refer to Section 7.5], where applicable
- Selected concomitant medications (CYP3A4 inhibitors and inducers)
- Relevant laboratory testing
- Occurrence of any SAEs/AESIs since last visit

#### 7.3. Effectiveness

#### 7.3.1. Effectiveness Endpoints

The primary effectiveness endpoints of this study are:

- Overall survival (OS): defined as the time from first treatment with pazopanib until death due to any cause;
- Progression free survival (PFS): defined as the interval between the date of first treatment with pazopanib and the earliest date of disease progression (by tumour response assessed by imaging or by clinical deterioration, whichever comes first) or death due to any cause;
- Overall Response Rate (ORR): defined as the percentage of patients with documented response [complete response (CR) or partial response (PR)] at any time.

#### 7.3.2. Effectiveness Assessment

See the Time and Events Table (Section 7) for the recommended schedule of assessments. Assessments are based on a calendar schedule and should not be affected by dose interruptions/delays. For post baseline assessments, a window of  $\pm$  4 weeks is permitted to allow for flexible scheduling and data entry.

As an observational study, no scans or procedures at enrollment and during follow-up are required or recommended per protocol. It is expected that evaluations such as bone and brain scans will be performed as clinically indicated (e.g., presentation of bone pain).

# 7.3.2.1. Follow-up Assessments for Patients Permanently Discontinued from Study Treatment

Refer to Section 4.2.1 Permanent Discontinuation from Study Treatment for follow-up assessment of patients who are to be followed up for disease progression and/or survival after permanently discontinuation from pazopanib.

#### 7.3.2.2. Assessment of Patient Completion

If the last radiographic assessment was more than 3 months prior to withdrawal from study and progressive disease has not been documented, if possible a disease assessment should be obtained recorded at the time of withdrawal from study.

#### 7.3.3. Guidelines for Evaluation of Disease

For the purposes of categorizing patients at enrollment in regards to the presence of measurable lesions, general guidance consistent with RECIST 1.1 is provided in Appendix 2.

# 7.3.4. Response Criteria

Since PRINCIPAL is not a clinical trial but an analysis of real world treatment population, no specific criteria for the evaluation of response (e.g., RECIST) is specified. Participating physicians are asked to assess tumour responses according to local processes and their own medical judgment. Because timing of assessments may be further apart than is seen in a typical RCT, any calculation of time to progression will be evaluated with appropriate caution and sensitivity analyses will be performed where feasible and relevant.

For the purposes of categorizing response in patients with measurable lesions, general guidance consistent with RECIST 1.1 is provided in Appendix 2.

# 7.4. Safety

# 7.4.1. Safety Endpoints

In addition to SAEs, the following adverse events of special interest (AESI) will be solicited:

- Any AE that results in a pazopanib dose modification or discontinuation
- Any other reports of the following AEs, regardless of their seriousness or severity:
  - Evidence of liver toxicity
  - New onset or worsened hypertension
  - Cardiac dysfunction
  - Thyroid dysfunction

#### 7.4.2. Adverse Events

The investigator or site staff will be responsible for detecting, documenting and reporting events that meet the definition of an AE or SAE as outlined in Section 7.3.

#### 7.4.2.1. Definition of an AE

Any untoward medical occurrence in a patient or clinical investigation patient, temporally associated with the use of a medicinal product, whether or not considered related to the medicinal product.

Note: An AE can therefore be any unfavorable and unintended sign (including an abnormal laboratory finding), symptom, or disease (new or exacerbated) temporally associated with the use of a medicinal product. For marketed medicinal products, this also includes failure to produce expected benefits, abuse, or misuse. Examples of events meeting the definition of an AE include:

- Exacerbation of a chronic or intermittent pre-existing condition including either an increase in frequency and/or grade of the condition
- New conditions detected or diagnosed after study treatment administration even though it may have been present prior to the start of the study
- Signs, symptoms, or the clinical sequelae of a suspected interaction
- Signs, symptoms, or the clinical sequelae of a suspected overdose of either study treatment or a concomitant medication (overdose per se will not be reported as an AE/SAE).

"Lack of effectiveness" or "failure of expected pharmacological action" *per se* is not to be reported as an AE or SAE. However, any signs and symptoms and/or clinical sequelae resulting from "lack of effectiveness" will be reported as an AE or SAE, if they fulfill the definition of an AE or SAE.

Events that **do not** meet the definition of an AE include:

- Medical or surgical procedure (e.g., endoscopy, appendectomy); the condition that leads to the procedure is an AE.
- Situations where an untoward medical occurrence did not occur (social and/or convenience admission to a hospital).
- Anticipated day-to-day fluctuations of pre-existing disease(s) or condition(s) present or detected at the start of the study that do not worsen.
- The disease/disorder being studied, or expected progression, signs, or symptoms of the disease/disorder being studied, unless more severe than expected for the patient's condition.

#### 7.4.2.2. Definition of a SAE

A serious adverse event is any untoward medical occurrence that, at any dose:

- a. Results in death
- b. Is life-threatening

NOTE: The term 'life-threatening' in the definition of 'serious' refers to an event in which the patient was at risk of death at the time of the event. It does not refer to an event, which hypothetically might have caused death, if it were more severe.

c. Requires hospitalization or prolongation of existing hospitalization

NOTE: In general, hospitalization signifies that the patient has been detained (usually involving at least an overnight stay) at the hospital or emergency ward for observation and/or treatment that would not have been appropriate in the physician's office or out-patient setting. Complications that occur during hospitalization are AEs. If a complication prolongs hospitalization or fulfills any other serious criteria, the event is serious. When in doubt as to whether "hospitalization" occurred or was necessary, the AE should be considered serious.

Hospitalization for elective treatment of a pre-existing condition that did not worsen from baseline is not considered an AE.

d. Results in disability/incapacity, or

NOTE: The term disability means a substantial disruption of a person's ability to conduct normal life functions. This definition is not intended to include experiences of relatively minor medical significance such as uncomplicated headache, nausea, vomiting, diarrhea, influenza, and accidental trauma (e.g. sprained ankle) which may interfere or prevent everyday life functions but do not constitute a substantial disruption.

e. Is a congenital anomaly/birth defect. Medical or scientific judgement should be exercised in deciding whether reporting is appropriate in other situations, such as important medical events that may not be immediately life-threatening or result in death or hospitalization but may jeopardize the patient or may require medical or

surgical intervention to prevent one of the other outcomes listed in the above definition. These should also be considered serious. Examples of such events are invasive or malignant cancers, intensive treatment in an emergency room or at home for allergic bronchospasm, blood dyscrasias or convulsions that do not result in hospitalization, or development of drug dependency or drug abuse.

# 7.4.2.3. Laboratory and Other Safety Assessment Abnormalities Reported as AEs and SAEs

Any abnormal laboratory test results (hematology, clinical chemistry, or urinalysis), or other safety assessments (e.g., ECGs, radiological scans, vital signs measurements) including those that worsen from baseline, and events felt to be clinically significant in the medical and scientific judgment of the investigator are to be recorded as an AE or SAE, in accordance with the definitions provided.

In addition, an associated AE or SAE is to be recorded for any laboratory test result or other safety assessment that led to an intervention, including permanent discontinuation of study treatment, dose reduction, and/or dose interruption/delay.

Any new primary cancer must be reported as an SAE.

However, any clinically significant safety assessments that are associated with the underlying disease, unless judged by the investigator to be more severe than expected for the patient's condition, are not to be reported as AEs or SAEs.

# 7.4.2.4. Disease-Related Events and/or Disease-Related Outcomes Not Qualifying as SAEs

An event which is part of the natural course of the disease under study (i.e., disease progression or hospitalization due to disease progression) does not need to be reported as an SAE. Death due to disease under study is to be recorded on the Discontinuation CRF form. However, if the underlying disease (i.e., progression) is greater than that which would normally be expected for the patient, or if the investigator considers that there was a causal relationship between treatment with study medication(s) or protocol design/procedures and the disease progression, then this must be reported as an SAE.

#### 7.4.2.5. Time Period and Frequency of Detecting AEs and SAEs

The investigator or site staff is responsible for detecting, documenting and reporting events that meet the definition of an AE or SAE.

SAEs and AESIs will be collected from the time the first dose of study treatment is administered until 30 days following discontinuation of pazopanib regardless of initiation of a new cancer therapy or transfer to hospice.

In addition, any SAE assessed **as related** to pazopanib or a GSK concomitant medication must be recorded from the time a patient consents to participate in the study up to and including any follow-up contact. All SAEs will be reported to GSK within 24 hours, as indicated in Section 7.4.2.6.

After discontinuation of study treatment, to the extent feasible, the investigator should monitor all AESIs/SAEs that are ongoing until resolution or stabilization of the event or until the patient is lost to follow-up.

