# Objective(s)

The primary objectives of the PRINCIPAL study are:

- 1. To evaluate overall survival (OS), progression-free survival (PFS) and the overall response rate (ORR) in patients treated with pazopanib;
- 2. To characterise the relative dose intensity (RDI) and its observed effect on treatment outcomes;
- 3. To characterise the RCC patient population treated with pazopanib (e.g., by demographics, disease characteristics, previous RCC treatment history) in comparison to a selected clinical trial population;
- 4. To evaluate the change in health-related quality of life (HRQoL) relative to baseline in patients treated with pazopanib; and
- 5. To evaluate the frequency of serious adverse events (SAEs) and adverse events of special interest (AESIs) in patients treated with pazopanib.

The secondary objectives of the PRINCIPAL study are:

- 1. To evaluate clinical effectiveness, safety and RDI in those patients treated with pazopanib with comparable baseline characteristics to those included in the Phase III clinical trial [VEG105192];
- 2. To evaluate clinical effectiveness, safety, RDI and HRQoL in relevant subgroups treated with pazopanib.

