# 4.2. Permanent Discontinuation from Study Treatment and Patient Completion Criteria

# 4.2.1. Permanent Discontinuation from Study Treatment

Patients will receive pazopanib at the discretion of the treating physician (e.g., until disease progression, death or unacceptable adverse event). The primary reason study treatment was permanently discontinued must be documented in the eCRF.

If the patient voluntarily discontinues from treatment due to toxicity, 'adverse event' should be recorded as the primary reason for permanent discontinuation in the eCRF.

All patients who permanently discontinue study treatment should be followed for progression, survival and new therapies according to the protocol schedule, for up to 30 months post-enrollment.

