# 9.2.4. Key Elements of Analysis Plan

The demographic and clinical profile of the study population will be described using baseline data. Continuous variables (e.g., age) will be reported as means, medians, ranges and standard deviations, as appropriate. Categorical variables (e.g., gender, race/ethnicity) will be summarized as number and percentage (%) of the total study population. Statistical analyses will be fully described in the written statistical analysis plan RAP. Evaluations and interpretations will be based on point estimates and 95% confidence intervals (CI) as evaluation of the statistical precision around the point estimate, where relevant. Effectiveness and safety analyses will be stratified by patient risk category, performance status (ECOG) and age (< 65 and  $\ge$  65 years) at enrollment, where relevant. Analyses may be additionally stratified by prior treatment, history of nephrectomy, histologic subtype and other characteristics as appropriate and as the distribution of characteristics allow. No formal hypothesis or statistical significance testing is planned. This approach follows the *Guidelines for Good Pharmacoepidemiology Practices*, Section D, point 10.

Data will be listed and summarized according to the GSK reporting standards, where applicable. Complete details will be documented in the RAP. Any deviations from, or additions to, the original analysis plan described in this protocol will be documented in the RAP and final study report.

As it is anticipated that accrual will be spread thinly across centers and summaries of data by center would be unlikely to be information, data from all participating centers will be pooled prior to analysis. All data up to the time of study completion/withdrawal from study will be included in the analysis, regardless of duration of treatment. There will be no imputation for missing data.

For the analysis of overall survival, the last date of known contact will be used for those patients who have not died at the time of analysis; such patients will be considered censored.

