#### 9.2.4.2.2. Adverse Events

Adverse events (AEs) will be coded using the standard Medical Dictionary for Regulatory Activities (MedDRA) and grouped by system organ class. AEs will be graded by the investigator according to the NCI-CTCAE (version 4.0).

Events will be summarized by frequency and proportion of total patients, by system organ class and preferred term. Separate summaries will be given for all AEs, drugrelated AEs, serious AEs and AEs leading to discontinuation of study treatment.

Characteristics (e.g. number of occurrences, action taken, grade, etc) of the following AEs of special interest will be summarized separately:

- Any adverse event that results in a pazopanib dose modification or discontinuation
- Any other reports of the following AEs:
  - Evidence of liver toxicity (e.g., increased ALT and/or AST, liver failure)
  - New onset or worsened hypertension
  - Cardiac dysfunction
  - Thyroid dysfunction
  - The incidence of deaths and the primary cause of death will be summarized

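### SAE and AESI frequencies are planned as crude proportions over a window set by time on pazopanib, so they mix event rate with exposure when groups are compared, and late SAEs enter only if judged related

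*Protocol*

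**What the plan says.** SAE and AESI frequency is a primary objective: "To evaluate the frequency of serious adverse events (SAEs) and adverse events of special interest (AESIs) in patients treated with pazopanib" (Protocol Summary, objective 5).

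Section 7.4.2.5 sets two collection windows.
- All SAEs and AESIs: from the time the first dose is "administered until 30 days following discontinuation of pazopanib regardless of initiation of a new cancer therapy".
- SAEs assessed as related to pazopanib or to a concomitant medication of the sponsor: these "must be recorded from the time a patient consents to participate in the study up to and including any follow-up contact".

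Section 4.2.1 leaves the length of treatment to the treating physician and follows patients who have stopped "for up to 30 months post-enrollment".

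The summary measure is in Section 9.2.4.2.2: "Events will be summarized by frequency and proportion of total patients", by system organ class and preferred term. Separate summaries are planned for all, drug-related and serious events and for events leading to discontinuation. Section 9.2.4.2.1 describes duration of treatment separately.

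On groups, Section 9.2.4 states: "Effectiveness and safety analyses will be stratified by patient risk category, performance status (ECOG) and age", where relevant. Section 9.2.4.1.2 adds, sample size permitting, a comparison of trial-eligible with non-eligible patients that covers safety.

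**The concern.** A patient's chance of contributing an event depends on the event rate and on how long events are collected. Here the collection time is time on drug plus 30 days, which can run from about one month to 30 months. A proportion of all patients has no term for that time. It is a fair description of the whole treated cohort. It is not a fair basis for setting poor-risk, frail or elderly patients beside others if the groups stay on drug for different lengths of time. The Protocol's rationale and design discussion name such under-represented patients as a reason for the study.

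The second issue is the unequal windows. Beyond 30 days after stopping, an unrelated SAE is not collected but a related one is. If both kinds go into one set of tables, the late period can only add to the related side.

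**Working it through.** **No figure to reproduce.** The Protocol gives no SAE or AESI rate, no precision for safety and no time on drug by subgroup. Everything below is illustration on assumed inputs.

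**Step 1: crude proportion at equal risk.** Assume a constant first-event hazard λ per month. Assume exponential time on drug T with median m, so μ = ln 2 / m. The collection window is min(T + 1, 30) months. Then

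P = 1 − [ e^(−λ) · μ/(λ+μ) · (1 − e^(−29(λ+μ))) + e^(−29μ) · e^(−30λ) ].

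| λ per month | median 3 months | median 9 months |
|---|---|---|
| 0.04 | 18.1% | 35.7% |
| 0.06 | 25.2% | 46.3% |

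Along each row the true risk per month is the same. Across rows, a short-exposure group with a 50% higher hazard (0.06 against 0.04) shows 25.2% against 35.7%. At a comparator hazard of 0.04, the short-exposure group would need about 2.4 times that hazard to show an equal proportion.

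**Step 2: sensitivity to the exposure gap.** Take 10.8 months, the pazopanib median PFS in VEG105192 (Section 1.1), as a stand-in for the longer median time on drug. Set λ = 0.03 in both groups.
- Median 3 versus 10.8 months: 14.1% versus 31.8%.
- Median 8 versus 10.8 months: 27.0% versus 31.8%.

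The distortion follows the difference in exposure and is modest when exposures are close.

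**Step 3: stopping caused by adverse events.** Section 7.4.1 counts any adverse event that leads to discontinuation as an AESI. Suppose 50% of the short-exposure group and 15% of the other stop for an adverse event. Let the rest follow Step 2 (medians 3 and 10.8 months).
- Short exposure: 0.50 + 0.50 × 14.1% = 57%.
- Long exposure: 0.15 + 0.85 × 31.8% = 42%.

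The ordering of the AESI proportions is now the opposite of Step 1.

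**Step 4: related share of SAEs.** Assume 30% of SAEs inside the window are related. Let late related SAEs occur at a fraction k of the on-drug related rate, with follow-up to month 30. The mean window W is 5.3 months (median 3 on drug) or 14.1 months (median 10.8). The on-drug rate cancels, so

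recorded share = [0.3W + 0.3k(30 − W)] / [0.3W + 0.3k(30 − W) + 0.7W].

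| k | median 3 months | median 10.8 months |
|---|---|---|
| 0 | 30% | 30% |
| 0.10 | 39% | 32% |
| 0.25 | 48% | 35% |

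For W = 5.3 and k = 0.10, the related part is 1.59 + 0.74 = 2.33 and the unrelated part is 0.7 × 5.3 = 3.72, so the share is 2.33/6.05 = 39%. Follow-up to 30 months for everyone is generous. With 20 months, the shares for k = 0.10 to 0.25 are 35% to 42% and 31% to 33%.

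**Step 5: what person-time does.** For first events, expected time at risk per patient is P/λ. In the reversed pair of Step 1 it is 0.252/0.06 = 4.2 months and 0.357/0.04 = 8.9 months. Events over time at risk return 6 and 4 per 100 patient-months, the true ordering. Under a constant hazard this holds by construction.

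**The case against.** The strongest reply is that Section 9.2.4.2 leaves complete safety details to the RAP, which is not shown, and that exposure-adjusted rates are ordinary RAP content. The study is descriptive and without hypothesis tests, and the objective asks for a frequency. The proportion of treated patients with an event on treatment plus 30 days is a valid quantity. Stratification and the eligibility comparison are both conditional.

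Much of this stands. A reader should not infer that no adjusted rate is planned, or that the crude proportion is wrong for the cohort as a whole. What remains is that the Protocol itself fixes the measure, the windows and the group contrasts, and those three do not fit together. The RAP may add a rate, but nothing in the Protocol asks for one.

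Four stronger readings are tempting and not supported.
- *Early stoppers always look safer.* Step 3 shows that toxicity-driven stopping can push the AESI proportion the other way.
- *Related SAEs are collected without limit.* They are recorded to any follow-up contact, and follow-up ends at 30 months. The extension does not apply to AESIs.
- *The safety results cannot be set against VEG105192.* No comparison of SAE or AESI frequency with that trial is planned. The planned comparisons with VEG105192 or a trial population concern RDI and patient characteristics, and the eligibility comparison is within this study.
- *The related share is certainly inflated.* The Protocol defines no ratio of related to all SAEs and does not say that late related events enter the same tables. With none, the share is unchanged.

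**Conclusion.** The point holds for between-group statements about safety and for any related-versus-all contrast among SAEs. It does not hold against the whole-cohort proportions as a description. In those contrasts the stated measure combines event rate with treatment duration, and the bias can go in either direction depending on why patients stop.

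The size is unknown from the Protocol. On assumed constant hazards it ranges from about 5 percentage points (medians 8 versus 10.8 months, λ = 0.03) to about 18 (medians 3 versus 9 months or 3 versus 10.8 months, λ = 0.03 to 0.04). At the wider gap, a 50% higher true rate can be hidden. The related share moves only if late related SAEs occur and are pooled with the rest. This is worth correcting before the analysis plan is final, but it does not threaten the study.

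**What to change.** In Section 9.2.4.2.2:
1. Keep the proportion of total patients as the whole-cohort description.
2. For SAEs and each AESI category, overall and in each safety stratum, add the event rate per patient-time at risk. Time at risk runs from first dose to the earliest of last dose plus 30 days, death or end of follow-up. State whether first events (time ending at the event) or all events are counted.
3. Base statements that compare strata, or trial-eligible with non-eligible patients, on these rates.
4. Restrict the SAE and drug-related SAE tables to that same window and list later related SAEs separately.

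Cumulative incidence with discontinuation as a competing event should not serve for the group comparison, because it still depends on time on drug. With λ = 0.06 and median 3 months against λ = 0.04 and median 9 months, λ/(λ+μ) · (1 − e^(−12(λ+μ))) gives 20.0% against 25.8% at 12 months, so the order is still reversed.

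The cost is some analysis wording and a few extra tables. Dose changes, discontinuations and deaths are already recorded with their dates, and event dates are needed in any case to apply the Section 7.4.2.5 window, so sites do nothing new. Person-time rates assume a roughly constant hazard and should be read beside the exposure summary of Section 9.2.4.2.1.
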